#### **4. Premature discontinuation, protocol violation or loss to follow-up**

All attempts will be made to enhance patient compliance. Early withdrawal may occur for any of the following reasons: a) the patient requests to; b) the investigator decides that it is in the patient's interest; c) a serious adverse event that is related to study medication; d) there is any other reason at the investigator's discretion. If the patient withdraws early, the patient will be encouraged to continue with scheduled visits. If they choose to not return, termination evaluations will be completed. If a patient is unable to return to the center, attempts will be made to follow the patient via telephone calls to complete the ALSFRS-R, adverse events and con meds until study completion.

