mg BID is a safe and tolerated dose in ALS patients. There are numerous studies of Memantine in other disease states at doses up to 60 mg a day that show good tolerability (31-34). The majority of side effects that were seen were dizziness, headache, fatigue and nausea. Therefore, this study will test whether a higher dose of Memantine, 20 mg BID would have a more significant slowing on disease progression in a randomized placebo-controlled Phase IIB trial. We feel the scientific background of Memantine with numerous proposed mechanism that could benefit ALS patients, and the results of our open label pilot trial, warrant studying Memantine at a higher dose to see if an effect can be demonstrated in a placebo-controlled trial.

The dose of 20 mg BID of Memantine has been studied in major depressive disorder, tension headache, bipolar disorder, nystagmus, diabetic neuropathy, and tremor. These studies found that dizziness, headache, fatigue, and nausea were the most common side effects. There were no clear drug related serious side effects seen in these studies to raise significant concern about using such a dose in a study of ALS patients. Discontinuation rates tended to be higher in patients on active drug and dizziness was the most common adverse event seen occurring in 20-25 percent of patients. These studies indicate that Memantine has been studied and shown to be safe even at doses as high as 60 mg a day; therefore we feel that ALS patients will tolerate 40 mg a day; however as stated in the tapering section of this proposal, patients will have options to down titrate if necessary.

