## **E. Specific Methods**

### **1. Study Schema (see table below in Appendix 1)**

#### *Visit Windows*

Study visits are based on a 28-day month, so if a patient comes in on a Monday, their next visit is 4 weeks (28 days) from that visit (on a Monday). Study visits are calculated from the baseline visit, which is the day the patient starts taking the medication. Maximum length of time between screening visit and baseline visit is 28 days but can be shorter as applicable.

As stated, visits from baseline are calculated on a 28-day month  $\pm$  7 days.

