6. FVC

7. Plasma for biomarker analysis
8. All medication collected

*Visit 12 Week 40*

1. Phone call to reconcile adverse events and concomitant medications.

*Unscheduled Visit (If needed)*

1. Assess and document all adverse events and concomitant medications.
2. Physical exam
3. CBC with differential and CMP labs, urine pregnancy test
4. Measure vital signs

*Early Termination (ET) Visit (If needed)*

1. Assess and document all adverse events and concomitant medications.
2. Physical exam
3. Administer the ALSFRS-R, ALS-CBS, NPI-Q, C-SSRS.
4. CBC with differential and CMP labs, urine pregnancy test
5. Measure vital signs

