**STUDY TABLE:**

Procedures	V1 SC	V2 BL	V3 Wk 4	V4 Wk 8	V5 Wk 12	V6 Wk 16	V7 Wk 20	V8 Wk 24	V9 Wk 28	V10 Wk 32	V11 Wk 36	V12 Wk 40
Consent	X											
Eligibility (Inclusion/Exclusion)	X											
Vitals	X		X		X			X			X	
Height	X											
Labs/Urine pregnancy test	X		X		X			X			X	
Med History	X											
Physical Exam	X		X		X			X			X	
FVC	X		X		X			X			X	
ALSFRS-R	X		X	X	X	X	X	X	X	X	X	
ALS-CBS	X		X		X			X			X	
NPI-Q	X		X		X			X			X	
C-SSRS	X		X		X			X			X	
Biomarkers	X		X		X			X			X	
Phone call				X		X	X		X	X		X
Drug dispensing		X	X		X			X				
Drug Acct			X		X			X			X	
Adverse Events			X	X	X	X	X	X	X	X	X	X
Concomitant Medication	X		X	X	X	X	X	X	X	X	X	X
Physician	X		X		X			X			X	
Study Coordinator	X		X	X	X	X	X	X	X	X	X	X
Data Entry	X		X	X	X	X	X	X	X	X	X	X

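### Patients who leave early and choose not to return have no scheduled safety contact after the termination visit, whereas completers are called at Week 40

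*Combined protocol and SAP*

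**What the plan says.** **Completers.** The Week 36 visit ends with "All medication collected". Visit 12 at Week 40 is a "Phone call to reconcile adverse events and concomitant medications". The Study Table carries both columns ("V11 Wk 36 V12 Wk 40") and marks adverse events and concomitant medication at Week 40.

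**Early leavers.** Section II.D.4 (Premature discontinuation, protocol violation or loss to follow-up) sets out three routes:

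1. "If the patient withdraws early, the patient will be encouraged to continue with scheduled visits".
2. "If they choose to not return, termination evaluations will be completed".
3. "If a patient is unable to return to the center, attempts will be made to follow the patient via telephone calls"; these calls cover the ALSFRS-R, adverse events and concomitant medication up to the end of the study.

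**The termination visit.** The Early Termination list in section II.E contains the same eight items as Week 36 and, like it, closes with drug return. No later call follows. Dosing Reduction/Discontinuation (section II.C) also matches this visit to Week 36 and mentions no counterpart to Week 40.

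**Events already known.** Dosing Reduction/Discontinuation and Recording Adverse Events both ask sites to try to follow an early-terminated patient who has not recovered until the event resolves. The serious adverse event section makes the site investigator responsible for managing events until resolution.

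**The concern.** Safety is a stated purpose of the trial (Study Type and Design), and the protocol says that this dose has not been studied in ALS patients (Statistical Power). After drug is stopped, a completer is actively asked about events. A patient who withdrew by choice is not asked again after the termination evaluations. An event or death in the following weeks is therefore sought in one group and left to chance in the other.

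This could matter for the comparison between arms as well as for completeness. On earlier studies of the same dose in other conditions, Conclusions from Open Label Study says: "Discontinuation rates tended to be higher in patients on active drug". If that pattern recurs here, and if those leavers tend to decline further visits, the group without a post-drug contact would be proportionally larger on memantine. The efficacy analysis would not make up for a missed death, because Statistical Methods treats deaths in the same way as drop-outs.

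**Working it through.** No sample-size or power figure bears on this point. The check sets the follow-up rules side by side, with a little arithmetic.

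**Post-drug interval for completers.** Visit Windows states that "visits from baseline are calculated on a 28-day month", with 7 days either way.
- Nominal: Week 40 − Week 36 = 4 weeks = 28 days.
- If the window applies to each visit: 28 − 7 − 7 = 14 days to 28 + 7 + 7 = 42 days.

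**Scheduled safety contact after drug is returned or the patient terminates**

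| How the patient leaves | Scheduled contact | Event still open | New event or death |
|---|---|---|---|
| Completes Week 36 | Week 40 call | Followed to resolution | Asked about at Week 40 |
| Withdraws, keeps visits | Remaining visits and calls | Followed to resolution | Asked about at each contact |
| Withdraws, unable to return | Attempted calls to study end | Followed to resolution | Asked about at each call |
| Withdraws, chooses not to return | None after termination evaluations | Followed to resolution | No planned contact |

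Only the last cell of the last row is empty. The rules for open events do not fill it, because they start from an event that is already known.

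**How many patients?** The documents give no expected drop-out for this trial and no share choosing not to return. The pilot gives only an all-cause figure (Results of Open Label Trial).
- 16 of 20 completed 6 months: (20 − 16)/20 = 20% did not.
- Applied to 90 patients: 0.20 × 90 = 18 early leavers, of whom 0.20 × 60 = 12 would be on memantine and 0.20 × 30 = 6 on placebo.

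These 18 are early leavers of every kind, in an open-label pilot at a lower dose and over a period shorter than 36 weeks. Some may have died, and others would fall under the first or third route. If p is the share of early leavers who choose not to return, the affected number at this rate is 18p, anywhere from 0 to 18. The documents do not fix p.

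**By arm.** The split of 12 to 6 comes from 2:1 allocation: it is 20% in each arm. A difference between arms needs unequal rates of leaving, or of declining to return. The documents suggest a direction for the first, from other conditions, and are silent on the second.

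**The case against.** The strongest reply is that the plan already protects the patients of most concern. Someone who stops because of an unresolved event is the person the open-event rules cover. A patient who must be terminated because an event persists after two dose changes has an open event by definition. Patients who withdraw are first encouraged to stay in follow-up, and those who cannot tolerate the lowest dose are asked to complete the study. Safety Variables also tells patients to report any adverse reaction to the site. What remains is a new event, after termination, in a patient who declined visits, would have accepted a call and did not report the event unprompted.

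Most of this stands, and it rules out three stronger readings that a reader might infer:

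- **That events are missed mainly in patients who stopped because of harm.** The open-event rules cover those patients for the event that made them stop.
- **That these patients have zero weeks of post-drug data where completers have four.** The plan does not tie the termination visit to the last dose, and adverse events are assessed at that visit, so some post-drug time may already be observed. What is zero is scheduled contact afterwards.
- **That events on memantine will be understated.** The discontinuation pattern comes from other conditions and says nothing about who declines to return.

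Nor does the lack of an early-termination column in the Study Table prove anything alone: the visit is specified in the text, and unscheduled visits have no column either.

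The reply does not close the gap. Self-reporting is passive, while completers are questioned. The serious adverse event rule covers events during the study, and no end of that period is stated for someone who has left, so even a volunteered event has no clear collection window.

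**Conclusion.** The gap is real but small. Followed exactly, the plan actively seeks new post-drug events and deaths in completers, in patients who keep their visits and in patients unable to return, but not in those who choose not to return. It concerns only events and deaths that begin after the termination visit in that subgroup.

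The number of patients cannot be derived from the documents. The figure of 18 early leavers illustrates all routes together and rests on carrying the pilot's 6-month completion over to this trial. Unequal ascertainment between arms is possible but not shown. The point rests on reading the telephone sentence in section II.D.4 as written, that is, as limited to patients unable to return.

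**What to change.** Extend the telephone follow-up in section II.D.4 to patients who choose not to return and have not refused contact. Add one call about 28 days after the last dose, with the Visit 12 content plus vital status, to three places: section II.D.4, the Early Termination list and the Study Table. Record the date of the last dose so that the interval can be computed.

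State in the analysis text that adverse events, serious adverse events and deaths will be tabulated by arm over one window for all patients, from first dose to 28 days after last dose. Report by arm how many patients could not be reached for the whole window.

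The cost is at most one coordinator call per affected patient, using the Week 40 content, and a line in the schedule. Some patients will decline, so the gap will shrink but not disappear. The change is to data collection only and leaves treatment, sample size and the primary analysis as they are.

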## **E. Specific Methods**

### **1. Study Schema (see table below in Appendix 1)**

#### *Visit Windows*

Study visits are based on a 28-day month, so if a patient comes in on a Monday, their next visit is 4 weeks (28 days) from that visit (on a Monday). Study visits are calculated from the baseline visit, which is the day the patient starts taking the medication. Maximum length of time between screening visit and baseline visit is 28 days but can be shorter as applicable.

As stated, visits from baseline are calculated on a 28-day month  $\pm$  7 days.

#### *Visit 1-Screening*

All patients must sign and date the most current Institutional Review Board (IRB)/Ethics Committee's approved written informed consent before any study specific assessments or procedures are performed. A screening examination (medical history and physical and neurological examination including vital signs, height and weight) will be performed.

Concomitant medications will be recorded

Laboratory blood tests will be assessed. A CBC with differential and comprehensive metabolic panel (CMP), will be attained using each site's local laboratory. CRP biomarkers will be drawn, processed and stored for batch shipping. A urine pregnancy test will be performed for females of childbearing potential. ALSFRS-R, ALS-CBS, NPI-Q, C-SSRS will be administered. The ALSFRS-R and Forced Vital Capacity will be used to also determine eligibility.

#### *Randomization*

After the patient fulfills screening criteria, data entered into the database, and their screening visit is monitored remotely, the patient will be randomized using a predetermined randomization formula. KUMC will provide the site with proper kit numbers for each randomized patient.

*Visit 2 –Baseline*

1. Dispense medication

Patients who are randomized will start at 10 mg per day for 2 week, and then titrate up to 20 mg twice daily over the next 7 weeks. One month (28 days) of Memantine or placebo will be supplied to the patient.

*Visit 3 – Week 4*

1. Assess and document all adverse events and concomitant medications.
2. Physical exam
3. Administer the ALSFRS-R, ALS-CBS, NPI-Q, C-SSRS.
4. CBC with differential and CMP labs, urine pregnancy test
5. Measure vital signs
6. FVC
7. Plasma for biomarker analysis
8. Two months of study medication will be supplied and prior medication collected. Drug accountability will be performed.

*Visit 4 – Week 8*

The study coordinator will contact patients by phone to assess the ALSFRS-R. Assess and document all adverse events and concomitant medications.

*Visit 5 – At Week 12*

1. Assess and document all adverse events and concomitant medications.
2. Physical exam
3. Administer the ALSFRS-R, ALS-CBS, NPI-Q, C-SSRS.
4. CBC with differential and CMP labs, urine pregnancy test
5. Measure vital signs
6. FVC
7. Plasma for biomarker analysis

8. Three months of study medication will be supplied and prior medication collected. Drug accountability will be performed.

*Visit 6 & 7 Telephone Contact – At Week 16 and Week 20*

The study coordinator will contact patients by phone to assess the ALSFRS-R. Assess and document all adverse events and concomitant medications.

*Visit 8 Week 24*

1. Assess and document all adverse events and concomitant medications.
2. Physical exam
3. Administer the ALSFRS-R, ALS-CBS, NPI-Q, C-SSRS.
4. CBC with differential and CMP labs, urine pregnancy test
5. Measure vital signs
6. FVC
7. Plasma for biomarker analysis
8. Three months of study medication will be supplied and prior medication collected. Drug accountability will be performed.

*Visits 9 & 10 Telephone Contact – At Week 28 and Week 32*

The study coordinator will contact patients by phone to assess the ALSFRS-R. Assess and document all adverse events and concomitant medications.

*Visit 11 Week 36*

1. Assess and document all adverse events and concomitant medications.
2. Physical exam
3. Administer the ALSFRS-R, ALS-CBS, NPI-Q, C-SSRS.
4. CBC with differential and CMP labs, urine pregnancy test
5. Measure vital signs
6. FVC

7. Plasma for biomarker analysis
8. All medication collected

*Visit 12 Week 40*

1. Phone call to reconcile adverse events and concomitant medications.

*Unscheduled Visit (If needed)*

1. Assess and document all adverse events and concomitant medications.
2. Physical exam
3. CBC with differential and CMP labs, urine pregnancy test
4. Measure vital signs

*Early Termination (ET) Visit (If needed)*

1. Assess and document all adverse events and concomitant medications.
2. Physical exam
3. Administer the ALSFRS-R, ALS-CBS, NPI-Q, C-SSRS.
4. CBC with differential and CMP labs, urine pregnancy test
5. Measure vital signs
6. FVC
7. Plasma for biomarker analysis
8. All medication collected

**F. Subject Safety and Data and Safety Monitoring Plan**

*Safety Variables*

A standard physical exam, including vital signs, will be performed at every in-person visit to ensure safety and to follow ALS progression. Laboratory tests will be performed at every in-person visit to monitor comprehensive metabolic values. Adverse Events (AEs) will be reviewed

and documented at every visit. Patients will be instructed to contact their PI or study coordinator with any adverse reactions they have regardless of causality to the medication. If patients have any adverse reactions believed to be caused from the medication, it will be the PIs discretion whether to reduce the patient's medication or to early terminate the patient from the study. At each visit, patients will be questioned about the development of any new symptoms. If an unscheduled visit is deemed necessary, the patient will be asked to return for a clinic visit within 48 hours. The site investigator will then evaluate any changes and determine the need for any intervention.

The C-SSRS is frequently asked for or recommended by various international agencies such as the FDA, WHO, JCAHO Best Practices Library, AMA Best Practices Adolescent Suicide, Health Canada, Korean Association for Suicide Prevention, Japanese National Institute of Mental Health and Neurology, and the Israeli Defense Force. The C-SSRS has been administered several million times and has exhibited excellent feasibility – no mental health training is required to administer it. The C-SSRS, initially designed for an NIMH-funded suicide study, addresses this goal by showing successful suicide attempt prediction not only in suicidal adolescents, but in non-suicidal adults as well. In the past, typical screening has only identified suicide attempts, omitting some of the most important behaviors that are critical for risk assessment and suicide prevention (e.g. collecting pills, buying a gun). The C-SSRS is the only screening tool that assesses the full range of evidence-based ideation and behavior items, with criteria for next steps (e.g. referral to mental health professionals); thus, the C-SSRS can be exceptionally useful in initial screenings. Training is required before administering the C-SSRS and must be completed and documented. The web-based training can be accessed at the following web site and takes approximately 30 minutes to complete.

<http://c-ssrs.trainingcampus.net/uas/modules/trees/windex.aspx>

### *Monitoring*

This study will utilize remote monitoring. After the patient is screened, all screening source documents and signed consent forms in their entirety will be sent to the Project Manager ([name] or alternate, [name]) at the University of Kansas Medical Center over a secured website. The University of Kansas Medical Center will retain the signed consent forms

and stored on a secure site. All other documentation will be destroyed. Sites will be asked to send source documentation periodically throughout the study.

Other items that the Project Manager will request and retain will be medical licenses or nursing licenses (if applicable), human subjects or GCP training, signed CV's of all key personnel, original 1572, laboratory director credentials, CV's, laboratory normative values and other documentation as needed. Each site is expected to maintain a regulatory binder with such documents and approvals.

#### *Laboratory Test Abnormalities*

In the event of medically significant unexplained abnormal laboratory test values, the tests should be repeated and followed up until they have returned to the normal range and/or an adequate explanation of the abnormality is found. For abnormalities that fall in the range of critical values that would affect safety then [name] will instruct the site to hold further treatment dosing. [name] will be notified within 24 hours of any unscheduled visits or SAEs. Once he is notified he will contact the DSMB to inform them if one of these events occurs.

#### *Treatment and Follow-up of AEs*

The site investigators will be responsible for reviewing laboratory results and serious adverse events to determine the relationship to the study medication. [name] and the Data and Safety Monitoring Board will determine whether changes in the protocol or consent form is needed based on reported AEs.

#### *Recording Adverse Events*

*Definition* - adverse events are clinical abnormalities (illness, signs, or symptoms) that begin or worsen during the course of the study and are not thought to be directly related to the expected course of ALS itself, whether or not the abnormality is believed by the investigator to be related to the study medication.

*Recording* - the investigator will monitor each patient closely and record all adverse events on the adverse event page of the case report form.

*Expectedness* - the investigator will determine whether the AE is expected or unexpected

*Severity* - adverse events should be graded for severity:

*Mild*: causing no limitation of usual activities

*Moderate*: causing some limitation of usual activities

*Severe*: causing inability to carry out usual activities

Adverse events should be followed up until they have stabilized or have returned to baseline status (in the event of a reaction to the medication). This is especially important for those events where the reported causal relationship to the study medication is anything other than “unrelated” (e.g. probable, possible). If patients have an adverse event that the PI assesses as “related” to the study medication then the PI will, or the patient can choose, to terminate the study or can decrease the dose of the medication by 10 mg per day. If the AE still does not abate then the PI or patient can again elect to terminate the study or decrease the dose by another 10 mg per day again. If the AE is still present after two dose titrations, then the patient must be terminated from the study. If the patient is terminated early, and the patient has not recovered from their adverse events, every effort should be made to follow the patient until the adverse event is resolved.

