### *Statistical Methods*

The primary comparison for efficacy will be based on a linear mixed effects (lme) model fit to the ALSFRS-R data for the 90 patients followed over 36 weeks. The model will be used to calculate fixed effects for intercept, placebo slope (rate of decline of ALSFRS-R) and change in slope for those treated with Memantine. Random effects included are for individual patient variation in intercept, slope and random error at each time point. The test for treatment effect is based on the change in slope due to treatment, as estimated by the model. Testing for significance is two-sided at a 10% level of significance. Analysis is limited to patients who receive at least one treatment dose and have at least 2 measurements (one at baseline and one after treatment). Deaths are treated the same as drop-outs. This model weighs each patient inversely by his estimated variance so that patients with missing values receive less weight than those with complete data.

We will also attempt to enrich the placebo group with historical controls with matching patients from the historical placebo database of 715 patients added to the 30 placebo patients from this trial. The historical controls will be selected to have same entry criteria as patients in this trial. There will be no patient-by-patient matching. We will first test whether the 30 patients from this trial differ from those in the historical database (using the same model with a term added to identify source: historical or contemporary). If this test finds that the two placebo groups differ, historical control will not be added and the combined placebo vs treated test will not be conducted. If the placebo control sets do not differ, the lme model described above will be fit to the combined data.

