of progression. Since it is impossible to identify if a patient is a fast or a slow progressor at randomization, small studies such as Carvalho's, or our previous pilot open label trial, can be skewed if a group of slow progressors are randomized to a placebo arm or a group of fast progressors are randomized to an active arm. We have attempted to modulate these effects somewhat by excluding patients who have had the disease for more than three years as possibly being slow progressors. In addition, we have excluded patients with significantly impaired FVC's, to try to limit the number of fast progressors. These measures are very standard in current ALS trials. Another limiting factor to both Carvalho's and our pilot study is that neither study analyzed the efficacy of Memantine at a higher dose. We feel that by using a higher dose of Memantine a more efficacious response may be seen even in a study which is relatively small. Another limitation to this study is 20mg/bid of Memantine has not been studied in ALS patients. Although 40, 50, 60 and even 80mg/d of Memantine have been studied in numerous other disease states and have been shown to be safe and tolerated, it is still unknown how this population will respond. However, we will assess carefully for safety and adverse events.

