### ***Reporting of Serious Adverse Events (Immediately Reportable)***

#### *Serious Adverse Events*

*Definition*: Serious adverse events are life threatening, fatal, result in hospitalization or prolonged hospitalization, permanent disability, congenital anomaly, cancer, or overdose, or are any event that the investigator believes is very unusual or potentially serious.

*Report*: Any serious adverse event will be reported immediately (within 24 hours). All serious adverse events will be recorded on the standard adverse events page of the case report form, and a serious adverse event form will be completed. The coordinating center will be notified within 24 hours.

*Follow-up of Adverse Events*: The site investigator is responsible for appropriate medical management and laboratory tests for adverse events until the event is resolved. The management and resolution of each adverse event should be recorded on the adverse event page of the case report form.

Any clinical AE or abnormal test value that is serious (defined as fatal or life-threatening, one which results in inpatient hospitalization, one which results in persistent disability, congenital anomaly or is medically significant or requires intervention to prevent one of the other outcomes listed), and which occurs during the course of the study, regardless of the treatment group, must be reported within one working day of the investigator becoming aware of the event. In addition, for fatal and life threatening events, the Medical Monitor ([name] at the University of Kansas Medical Center) should be contacted immediately. The chair of the Data and Safety Monitoring Board ([name], Neurologist at University of Buffalo), and the DSMB, will review SAEs in a similar manner and make a determination if the patient can continue in the trial. If the subject needs to stop study medication [name] will contact the PI and study coordinator at that subjects' site.

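### The AE definition lets ALS-like drug effects such as fatigue go unrecorded, and the SAE section does not settle whether ALS-attributed deaths and serious events must be reported

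*Combined protocol and SAP*

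**What the plan says.** **AE definition (Recording Adverse Events).** An AE is a clinical abnormality that starts or gets worse on study and is "not thought to be directly related to the expected course of ALS itself". This applies "whether or not the abnormality is believed by the investigator to be related to the study medication". The investigator is then to "record all adverse events on the adverse event page of the case report form".

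**SAE wording (Serious Adverse Events).** Two descriptions stand in the same section.
- The opening definition begins "Serious adverse events are life threatening, fatal, result in hospitalization or prolonged hospitalization". It ends with an open category for anything the investigator regards as out of the ordinary or possibly serious. It mentions no ALS exception.
- The later reporting paragraph covers "Any clinical AE or abnormal test value that is serious". It goes on to require immediate contact with the Medical Monitor for fatal and life-threatening events, and DSMB review of SAEs.

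**Related text.** Conclusions from Open Label Study reports that "dizziness, headache, fatigue, and nausea were the most common side effects" at this dose in other conditions. The limitations discussion under Statistical Power says that "20mg/bid of Memantine has not been studied in ALS patients" and offers careful safety and AE assessment in response. In Statistical Methods, "Deaths are treated the same as drop-outs".

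**The concern.** Study Type and Design presents the trial as evaluating safety as well as efficacy, and AE assessment is the protocol's stated answer to using a dose untried in ALS. An attribution made before recording weakens that answer, because an event that was never written down cannot be recovered at analysis. The drug effects most exposed are those that look like the disease.

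Two things are at stake. One is the between-arm comparison of non-serious AEs. The other is whether the DSMB sees a complete and consistent account of deaths and serious events. Under Treatment and Follow-up of AEs, decisions on changing the protocol or consent form rest on the AEs that are reported.

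**Working it through.** The documents give no AE, SAE or death rate, so there is no plan figure to reproduce. The check is mainly a comparison of texts.

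**1. Non-serious events.** The definition has two limbs: the event is new or worse, and it is not thought to follow directly from the expected course of ALS. The drug-relatedness clause says only that drug causation is not needed for AE status; it does not bring back an event that fails the second limb. Only AEs go on the AE page. Followed as written, fatigue put down to expected ALS is not recorded, even if the drug caused it. An event not thought to be directly due to ALS stays an AE.

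**2. Serious events.**

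| Text in Serious Adverse Events | Depends on the term AE? | ALS exception stated? |
|---|---|---|
| Opening definition (fatal, life-threatening, hospitalisation, open category) | Only through the name serious adverse event | No |
| Later paragraph (serious clinical AE or abnormal test value) | Yes, for clinical events | Not stated, but could be inherited |
| Immediate contact for fatal and life-threatening events | Follows the later paragraph | No |

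The two wordings also differ in other ways. One requires reporting within 24 hours and the other within one working day, and their lists of criteria are not the same. One site could report an ALS-attributed death under the opening definition. Another could leave it out by reading the later paragraph together with the AE definition. Study Type and Design names 14 centers.

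**3. Whether another route captures the loss.**
- Safety Variables has patients asked about new symptoms at each visit. That elicits the symptom, but recording it as an AE still depends on the definition.
- Laboratory Test Abnormalities passes unscheduled visits to the DSMB. A death at home need not produce such a visit.
- The Study Table schedules ALSFRS-R at screening and nine post-baseline visits, and FVC at screening and weeks 4, 12, 24 and 36. These track decline without any attribution step, but no section sends them to the DSMB.
- Statistical Methods handles deaths as drop-outs in the slope model and describes no mortality comparison by arm. The Study Table has no vital-status row.

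**4. Illustration (all rates assumed).** Let true fatigue rates be 25% on memantine and 15% on placebo, and let f be the fraction set aside as ALS, equal in both arms.

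Recorded excess = (1 − f) × (25 − 15) points.
- f = 0: 10 points.
- f = 0.5: 12.5 − 7.5 = 5 points.
- f = 1: 0 points.

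Recorded ratio for f below 1 = 25(1 − f) / 15(1 − f) = 1.67, unchanged.

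With 60 memantine and 30 placebo patients (90 at 2:1), the expected patients with fatigue are 60 × 0.25 = 15 and 30 × 0.15 = 4.5. At f = 0.5 they become 7.5 and 2.25, so fewer events remain on which to base any comparison. If the fractions differ by arm (f_M on memantine, f_P on placebo), the ratio becomes 1.67 × (1 − f_M)/(1 − f_P), which can move either way.

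**The case against.** The strongest reply is that the opening SAE definition stands on its own. It lists fatal and life-threatening events and has an open category, with no ALS exception. Reporting is within 24 hours, the Medical Monitor is contacted at once for fatal events, and the DSMB reviews SAEs. A reader might infer from the AE definition that ALS-attributed deaths fall outside SAE reporting altogether. The documents do not support that; they support only that the later wording permits such a reading and nothing rules it out.

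The exclusion is also narrower than everything attributed to ALS, since decline faster than expected is not on its face the expected course. Faster decline is what the two-sided ALSFRS-R test and the FVC series measure. A reader might add weakness and respiratory decline to the drug effects at risk, but the protocol's list of common memantine effects names neither. The drop-out sentence concerns the efficacy model and does not govern safety reporting; it matters here only because no other mortality comparison is described.

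Finally, separating expected progression from AEs is a deliberate choice that keeps reporting manageable. That is a fair aim, but an attribution field serves it without discarding the event.

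What survives is the loss of non-serious ALS-like effects, which follows from the definition itself, and the unresolved conflict over serious events.

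**Conclusion.** The concern holds in two limited parts. First, non-serious drug effects resembling ALS, with fatigue as the documented example, can go unrecorded because of an unadjudicated judgement made before recording. Second, the AE and SAE sections do not say whether the exclusion reaches deaths and other serious events, so reporting of ALS-attributed ones can differ between sites.

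The size cannot be calculated from the documents. Under equal misattribution in both arms, the absolute excess shrinks in proportion to the fraction set aside. A reader might infer that relative comparisons are also biased toward no difference, but under that assumption the ratio does not change; what is lost is events, and so precision. Unequal misattribution would shift the ratio in a direction the documents do not determine.

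This is a cheap improvement worth making, not evidence that mortality is hidden from the DSMB.

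**What to change.** - **Recording Adverse Events:** replace the ALS exclusion with recording of every new or worsening event, and add a yes/no field for attribution to the expected course of ALS beside the drug-relatedness assessment.
- **Serious Adverse Events:** reconcile the two wordings with each other and with the AE definition. State that all deaths and other serious events are recorded, reported and reviewed by the DSMB whatever their attribution to ALS.
- **Statistical Methods:** add tables of AEs, SAEs and deaths by arm, with and without ALS-attributed events.

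The cost is protocol wording, one case report form field and a few tables. The downside is more AE forms for expected disease events; the attribution field lets these be separated at analysis.
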